### **Method of Detecting AEs and SAEs**

Care will be taken not to introduce bias when detecting AEs and/or SAEs. Open-ended and non-leading verbal questioning of the participant is the preferred method to inquire about possible AEs.

### **Follow-up of AEs and SAEs**

ZELTIQ P/N: [REDACTED]

Protocol Number: ZA17-005

This document and the contents hereof are considered proprietary and confidential information of ZELTIQ Aesthetics, Inc. Disclosure to unauthorized individuals or dissemination, publication or copying is prohibited without prior written consent of ZELTIQ.

After the initial AE/SAE report, the investigator is required to proactively follow each participant at subsequent visits/contacts. All SAEs will be followed until resolution, stabilization, the event is otherwise explained, or the participant is lost to follow-up.

The investigator is obligated to perform or arrange for the conduct of supplemental measurements and/or evaluations as medically indicated or as requested by the sponsor to elucidate the nature and/or causality of the AE or SAE as fully as possible. This may include additional laboratory tests or investigations, histopathological examinations, or consultation with other health care professionals.

New or updated information will be recorded in the originally completed CRF.

The investigator will submit any updated SAE data to the sponsor within 24 hours of receipt of the information.

### **Reportable Incidents**

Serious adverse events (SAEs) and unanticipated adverse device effects (UADEs) must be reported within 24 hours of knowledge of the event to the Sponsor.

All adverse events observed by the investigator or reported by the subject will be recorded on the appropriate CRF, irrespective of relationship to CoolSculpting and KYBELLA®, as well as the KYBELLA® skin grid. Medically significant adverse events will be followed until resolved or considered stable. For each event, the investigator will record a description, dates of onset and resolution, severity, and relationship to CoolSculpting, KYBELLA® and KYBELLA® skin grid. The investigator may be required to provide follow-up information.

Any adverse event that results in withdrawal from the study must be reported to the Sponsor after the decision to withdraw the subject is made.

Any death occurring during the study must be reported to the Sponsor within 24 hours of the discovery of the event. This includes any death that occurs within 30 days after the subject's final visit, irrespective of when the final visit occurs.

### **Assessment of Severity**

Severity of adverse events will be determined using the following scale:

- **Mild:** Event that is easily tolerated and may require only minimal treatment or therapeutic intervention. The event does not generally interfere with usual activities of daily living.

- Moderate: Events that interfere with usual activities of daily living, causing discomfort but poses no significant or permanent risk of harm to the research participant. It is usually alleviated with additional specific therapeutic intervention.
- Severe: Event that is incapacitating, with inability to work and do the usual activities of daily living, or significantly affects clinical status. This may require intensive therapeutic intervention.

### Assessment of Causality

- The investigator is obligated to assess the relationship between study treatment and each occurrence of each AE/SAE.
- A *reasonable possibility* of a relationship conveys that there are facts, evidence, and/or arguments to suggest a causal relationship, rather than a relationship cannot be ruled out.
- The investigator will use clinical judgment to determine the relationship.
- Alternative causes, such as underlying disease(s), concomitant therapy, and other risk factors, as well as the temporal relationship of the event to study treatment administration will be considered and investigated.
- The investigator will also consult the investigator's brochure and/or product information, for marketed products, in his/her assessment.
- For each AE/SAE, the investigator must document in the medical notes that he/she has reviewed the AE/SAE and has provided an assessment of causality.
- For each AE/SAE, there are 5 levels of causality, as follows:
  - Not related
  - Unlikely
  - Possible
  - Probable
  - Causal relationship

- There may be situations in which an SAE has occurred and the investigator has minimal information to include in the initial report to the sponsor. However, it is very important that the investigator always make an assessment of causality for every event before the initial transmission of the SAE data to the sponsor.
- The investigator may change his/her opinion of causality in light of follow-up information and send an SAE follow-up report with the updated causality assessment.
- The causality assessment is one of the criteria used when determining regulatory reporting requirements.

The investigator will determine the relationship of each adverse event to CoolSculpting and/or KYBELLÀ® using the question: "Is there a reasonable possibility that the event may have been caused by treatment with CoolSculpting and/or KYBELLÀ®? Answer 'yes' or 'no' for each adverse event."

The guideline below should be used to consider relatedness:

For a "no causal relationship" assessment, the adverse event:

- May be judged to be due to extraneous causes such as disease or environment or toxic factors
- May be judged to be due to the subject's clinical state or other therapy being administered
- Is not biologically plausible
- Does not reappear or worsen when CoolSculpting and/or KYBELLÀ® is re-administered
- Does not follow a temporal sequence from treatment with CoolSculpting or administration of KYBELLÀ®

For a causal relationship (including unlikely, probable and possible assessments) there is a reasonable possibility that the event may have been caused by CoolSculpting, KYBELLÀ® and/or the KYBELLÀ® Grid. The adverse event:

- Follows a temporal sequence from treatment with CoolSculpting and/or administration of KYBELLÀ®
- Is a known response to CoolSculpting and/or KYBELLÀ® based on clinical or nonclinical data

- Could not be explained by the known characteristics of the subject's clinical state, environmental or toxic factors, or other therapy administered
- Disappears or decreases upon cessation of CoolSculpting and/or KYBELLA® tx or reduction in total dose of KYBELLA®
- Reappears or worsens when CoolSculpting and/or KYBELLA® is re-administered

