**Figure 3: Molecular Structure of Synthetic Deoxycholic Acid**

**Figure 4: Representative packaging of KYBELL® 2 mL vials**

ZELTIQ P/N: [REDACTED]  
Protocol Number: ZA17-005

This document and the contents hereof are considered proprietary and confidential information of ZELTIQ Aesthetics, Inc. Disclosure to unauthorized individuals or dissemination, publication or copying is prohibited without prior written consent of ZELTIQ.

- At the discretion of the investigator, topical or local anesthesia (e.g., topical or injectable lidocaine preparations without epinephrine, ice) may be applied in the planned treatment area and any medications will be recorded on the appropriate case report form (CRF).
- [REDACTED]  
[REDACTED]  
[REDACTED] A grid, specifically developed to be applied to the treatment area to guide the placement of injections, will be used.
- For each KYBELLÀ® injection, the investigator will palpate the treatment area to determine the approximate thickness of the targeted SMF and inject KYBELLÀ® into fat tissue at a depth of approximately mid-way into the SMF.
- If at any time resistance is met as the needle is inserted, indicating the possibility of contact with fascial or nonfat tissue, the needle will be withdrawn to an appropriate depth before the injection is given.
- Upon needle withdrawal, pressure will be applied to each injection site as necessary to minimize bleeding; an adhesive dressing may be applied. Upon completion of the injections, the area may be gently massaged.
- At each treatment session, the investigator will determine the number and locations of injections. He or she will evaluate each planned injection location to avoid sites for which an injection may not be appropriate (e.g., nodule formation, significant residual inflammation, other adverse event that warrants a delay, or lack of SMF).
- [REDACTED]  
[REDACTED]

Subjects may be discharged from the research facility approximately 30 minutes after KYBELLÀ® is administered, provided it is medically appropriate to do so.

At no time is the dilution of KYBELLÀ® permitted.

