### 2.14.1. **Primary Endpoints**

The primary endpoints of the study will be defined as follows:

- Safety endpoint: incidence of device, drug or procedure-related adverse events.
- Efficacy endpoint:
  1. The reduction, from baseline (CR-SMFRS =4) to final follow-up, of submental fat (SMF) as assessed by the proportion of subjects who have at least a 1-grade improvement on the Clinician Reported Submental Fat Rating Scale (CR-SMFRS), and
  2. The reduction, from baseline (CR-SMFRS=4) to final follow-up, of SMF as assessed by the proportion of subjects who have at least a 2-grade improvement on the CR-SMFRS.

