## 2.15.2. Analysis Population

Analysis Populations are defined as following:

Per-protocol Population (PP):

The Per-protocol Population will consist of all the treated subjects followed through to the final post-treatment visit and with weight change of no more than five percent at the time the final post-treatment visit images are taken. Since a weight change of more than 5 percent will affect the images, the primary Efficacy analysis will be performed based on this study population. Subjects who do not complete the treatment or had an interruption in the treatment will not be included in the primary and secondary Efficacy analyses.

As-Treated Population (AT):

This population consists of all treated subjects regardless of whether they become pregnant, undergo weight change during the study, or had interrupted treatment.

Safety Population (SA):

This population will consist of all the treated subjects with safety evaluation after the treatment. This population should be identical to the AT population. The safety data analyses will be performed based on the Safety Population.

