## 2.15.3. Endpoint Analysis

### 2.15.3.1. Primary Safety Endpoint:

The primary safety endpoint is incidence of all device, drug – and/or procedure-related adverse events. All adverse events reported during and following the treatment will be included in the safety analysis. The frequency and proportion of subjects reporting each type of adverse event will be tabulated by relationship with the treatment and seriousness as well as severity of the event.

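### The primary safety endpoint counts procedure-related events, but no causality item asks about study procedures, and the relatedness rules are not reconciled

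*Combined protocol and SAP*

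**What the plan says.** Section 2.14.1 defines the primary safety endpoint as "incidence of device, drug or procedure-related adverse events". The Protocol Summary and Section 2.15.3.1 name the same three sources. Section 2.15.3.1 adds that the "proportion of subjects reporting each type of adverse event will be tabulated by relationship with the treatment", and Section 2.15.2 states: "The safety data analyses will be performed based on the Safety Population".

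Relatedness is collected in Section 2.18, in several places:

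- **Reportable Incidents** has the investigator record for each event, among other items, "severity, and relationship to CoolSculpting, KYBELLA® and KYBELLA® skin grid".
- **Assessment of Causality** sets a five-level scale, then has relatedness determined by one yes/no question: "Is there a reasonable possibility that the event may have been caused by treatment with CoolSculpting and/or" KYBELLA. Its guideline for a negative answer includes events judged to be due to the subject's clinical state "or other therapy being administered".
- **The guidance on a positive answer**, which follows, adds the KYBELLA grid and places unlikely, as well as possible and probable, on the causal side.
- **Serious Adverse Event Reporting Procedures** calls for a separate form per drug or device, for serious events only.

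The opening text of Section 2.18, on the investigator's follow-up duties, names study procedures as a source of related events distinct from study treatment. Section 1.2.2 says that at the KYBELLA session "topical or local anesthesia (e.g., topical or injectable lidocaine preparations without epinephrine, ice) may be applied".

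**The concern.** An incidence of related events is only as good as the item that decides what is related. Here the endpoint has three sources, and the items that feed it name two products and, in one place, the grid. The procedure part of the endpoint has no defined origin. An investigator who follows the text has nowhere to put an event caused by the anesthesia or another procedural step.

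The rule for turning a causality judgment into related or not related is also stated in more than one way, so two investigators could classify the same event differently.

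Product-level attribution matters as well, because the study is about using two products in sequence. At stake is what the primary safety endpoint counts, and whether its tables can say which component an event belongs to.

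**Working it through.** The plan gives no expected rate, margin or test for the safety endpoint, so it has no figure to reproduce. The check is a comparison of sections plus simple arithmetic.

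**1. Sources in the endpoint against sources asked about**

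| Source | Endpoint (2.14.1, 2.15.3.1) | Recorded (2.18, Reportable Incidents) | Yes/no question (2.18, Assessment of Causality) |
|---|---|---|---|
| CoolSculpting | yes, as device | yes, separately | yes, pooled |
| KYBELLA | yes, as drug | yes, separately | yes, pooled |
| Skin grid | not named | yes, separately | no (only in the guidance that follows) |
| Study procedure | yes | no | no |

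The last row is the gap. A reaction due only to lidocaine or ice is caused by neither product. The literal answer to the question is no, yet the event is related to the procedure.

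**2. Size of the gap**

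The input is the maximum of 20 treated subjects (Sections 2.6 and 2.15.3.5). One subject whose only related event is procedural changes the incidence by 1/n: 1/20 = 0.05, or 5 percentage points. With fewer subjects the step is larger. The documents give no expected number of such subjects, so the total effect cannot be computed.

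**3. Which judgments count as related**

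The scale has five levels and the question has two answers, with no stated mapping between them. The later guidance counts unlikely as causal. An investigator who rates an event unlikely could reasonably answer no to the question, while the guidance would count it. One subject whose only event is of this kind again moves the incidence by 1/20 = 5 points, but upward if the guidance is followed.

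**4. Overlap of the two products**

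Section 6.2 expects CoolSculpting sensory changes to resolve within 12 weeks and does not count them as adverse events. The first KYBELLA session comes 6 weeks, plus or minus 7 days, after the second CoolSculpting treatment (Section 2.11.3), which is 5 to 7 weeks. The possible overlap is 12 − 7 = 5 weeks to 12 − 5 = 7 weeks. Section 6.2 lists numbness as a KYBELLA adverse reaction. Whether numbness in that window is counted can therefore depend on which product it is attributed to.

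**5. Denominator for KYBELLA- and grid-related events**

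Treatment starts with cold therapy (Section 2.10), and the Safety Population is the treated subjects with a safety evaluation (Section 2.15.2). Section 2.11.3 sends only subjects graded 3 or 2 on the CR-SMFRS to injection. Subjects with another grade, and those who leave before that visit, can be in the denominator without having been injected.

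With the same numerator, the rate among injected subjects divided by the rate among all treated equals (number treated)/(number injected). The number injected is not given. Assuming 20 treated, for illustration:

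- 18 injected: 20/18 = 1.11
- 14 injected: 20/14 = 1.43
- 10 injected: 20/10 = 2.00

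**The case against.** Much can be said for the plan.

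- **Pooling.** A reader might infer that the pooled question cannot deliver the endpoint. The documents do not support that. The endpoint is a union, and a pooled yes answers device or drug directly.
- **Splitting by product.** A reader might also infer that a pooled yes can never be split. Reportable Incidents requires relationship to each product and the grid for every event, and serious events have a form per product. If these are completed separately, product-level attribution exists. What stands is the conflict between that recording and the pooled question.
- **Other therapy.** The phrase could be read as sending every anesthetic reaction to not related. It more naturally means concomitant, non-study therapy, which the same section names as an alternative cause, and it is guidance rather than an automatic rule. It needs clarifying, but the gap does not depend on it.
- **Width of the gap.** Section 6.2 already attributes vacuum pressure, discomfort during the procedure and applicator dermatitis to CoolSculpting, and the adverse device effect definition covers use errors. The certain gap is causes outside both products, chiefly anesthesia. Such events still appear in the tables, because Section 2.15.3.1 includes all adverse events. They are missed only in the related count.
- **Denominator.** All treated subjects is a legitimate base for a sequential regimen, and Section 1.1 plans at least one KYBELLA session. The rate among injected subjects is not the true rate; it answers a different question. That supports adding it, not substituting it.

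The case report form is not in the documents, so it may already hold a procedure field. The protocol text does not require one.

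**Conclusion.** The concern holds in a limited form. The primary safety endpoint includes procedure-related events, and neither the relationships to be recorded nor the causality question captures them, although Section 2.18 itself treats study procedures as a separate source. Each affected subject moves the incidence by 5 percentage points at 20 treated. How many would be affected is unknown.

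The pooled question, the per-product recording, the five-level scale and the placing of unlikely under causal are not reconciled, so the numerator is ambiguous.

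A reader might conclude that these faults all make the regimen look safer. The documents do not support that: the missing procedure item lowers the related count, while counting unlikely as causal raises it. The net direction is not established.

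The denominator is a reporting gap whose size rests on the number injected. The factors of 1.11 to 2.00 are illustrations, not projections. The conclusion assumes that the form follows the protocol text.

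**What to change.** 1. In Section 2.18, under both Reportable Incidents and Assessment of Causality, ask relatedness separately for CoolSculpting, KYBELLA, the skin grid and study procedure, with anesthesia named under the last.
2. In the guideline for a negative answer, state that other therapy means non-study therapy.
3. State which of the five levels count as related for the endpoint, and reconcile the scale, the yes/no question and the guidance that places unlikely under causal.
4. In Section 2.15.3.1, keep the figure over all treated subjects. Beside it, report KYBELLA- and grid-related events over subjects who received at least one KYBELLA session, and give the number injected.

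The cost is one case report form field, one table column and a few lines of protocol text. Reported related-event percentages may be slightly higher. The change is best made before data collection, since procedure attribution may not be reliably recovered afterwards.

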### Serious Adverse Event Reporting Procedures

All serious adverse events must be reported to the Sponsor within 1 working day of discovery or notification of the event and according to IEC/IRB requirements and the institution at which the study is conducted, if applicable. Serious adverse event information and any follow-up information will be recorded on a Serious Adverse Event Form and transmitted to the Sponsor using the contact information provided by the Sponsor. Note that for each drug/device used in this study, a separate SAE form and contact information will be used. The Sponsor will be responsible for evaluating and reporting any serious adverse events and suspected unexpected serious adverse reactions in accordance with all applicable laws and regulations.

### Safety Monitoring Considerations

If an adverse event occurs that in the judgment of the investigator represents a potential risk for new subjects, the investigator will contact the Sponsor within 1 working day after becoming aware of the event.

A full reporting of the event shall be provided within 10 working days of the event. The Sponsor is then responsible for notifying the IRB, as required.

### Pregnancy

- Details of all pregnancies in female participants will be collected after the start of study treatment through the duration of the pregnancy.
- If a pregnancy is reported, the investigator should inform the sponsor within 24 hours of learning of the pregnancy.
- If a female of childbearing potential becomes pregnant during the study, the investigator should notify the participant's physician that the participant may have been treated with KYBELLA® and/or CoolSculpting and exit the participant from the study.
- Abnormal pregnancy outcomes (e.g., spontaneous abortion, fetal death, stillbirth, congenital anomalies, ectopic pregnancy) are considered SAEs.

ZELTIQ P/N: [REDACTED]

Protocol Number: ZA17-005

- A pregnancy form will need to be filled out by the site and submitted to the sponsor.

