## **2.9. *Screening Procedures***

### **2.9.1. *Screening Visit; Required; Week -4 to Day 0***

The subject shall be consented for study participation as described in Section 2.8. After the informed consent form is signed, subjects will be screened for eligibility. Each subject will be evaluated to determine that all eligibility criteria are met. The investigator or designee shall complete a brief medical history and examine the subject to confirm eligibility for the study.

1. Obtain Subject Self-Rating Scale score.
2. Obtain height and weight.
3. Evaluating investigator to assess intended treatment area and determine severity of submental fullness based on Clinician Reported-Submental Fat Rating Scale (CR-SMFRS).
  - a. Subjects must score a 4 (extreme) in order to be enrolled.
4. Assess oral cavity for current dental infection or evidence of dry mouth.
5. Assess function of the marginal mandibular nerve (grimace with ability to show lower teeth) and hypoglossal nerve (tongue does not deviate upon protrusion).

6. Assess upper neck to rule out enlarged lymph nodes or glands.
7. Assess for dermatological conditions that may lead to exclusion of the subject from the study.
8. Document subject's medication use (including over-the-counter medications, vitamins and herbs), Fitzpatrick Skin Type, and ethnicity, as well as any skin irregularities (e.g. moles, birth marks, scars, discoloration).
9. All female subjects of childbearing potential will be asked to take a pregnancy test (urine) prior to being treated. If the subject is pregnant, she will be excluded from participation.

Female subjects of childbearing potential will be advised to avoid becoming pregnant during the course of the study by agreeing to practice adequate contraception, in the judgement of the investigator, during the course of the study. If the subject becomes pregnant during the course of the study, she will not be treated subsequently with the study device or drug and she will be required to have follow-up photographs and ultrasounds. She will also be asked for information about the pregnancy and the birth of the child.

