All subjects will be asked to maintain their weight by not making any major changes to their diet or exercise regimen during the course of the study. If the weight change is more than 5% at the final visit, the subjects' data will be excluded from the primary Efficacy analyses. Subjects who do not maintain their weight within 5% will continue in the study, however their data will be excluded from Efficacy analyses.

Subjects who meet all of the inclusion criteria and none of the exclusion criteria shall be eligible to participate in the study and the first treatment will be scheduled.

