**Figure 5. Subject enrollment and study flow.**

**Table 2. Schedule of assessments.**

	Screening (< 1 hr)	Treatment Visit 1 (< 3 hrs)	Treatment Visit 2 (< 3 hrs)	Treatment Visit 3 (< 3 hrs)	Treatment Visit 4 (Optional) (< 3 hrs)	2 Week Follow-Up (< 1 hr) †	Final Follow-Up (< 1 hr)
Time Frame	Day - 30 to 0	Day 0	6 ± 1 weeks post last tx	6 ± 1 weeks post last tx	4-7 weeks post last tx	2 weeks ± 3 days post each tx	12 ± 3 weeks post final tx
Informed Consent*	X						
Inclusion/Exclusion Criteria	X	X	X	X	X		
Pregnancy Test	X	X	X	X	X		
Medical History	X						
Tx Site Assessment	X	X	X	X	X	X	X
Oral Cavity Assessment	X		X	X	X	X	X
Nerve Function Assessment	X		X	X	X	X	X
Height	X						
Weight	X	X	X	X	X	X	X
CR-SMFRS Assessment	X			X	X		X
Photography	**X	X	**X	X	**X	**X	X
Ultrasound		X		X			X
CoolMini Treatment		X	X				
KYBELLA® Treatment				X	**X		
[REDACTED]		X	X	X	X	X	X
AE Assessment		X	X	X	X	X	X
Subject Self Rated Scale	X			X			X

\* Informed consent to be signed by subject prior to the collection of any data or completion of any study procedures.

\*\* Optional

† Follow-up after each treatment

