### **Time Period and Frequency for Collecting AE and SAE Information**

All AEs and SAEs from the signing of the ICF until the last follow-up visit will be collected at the timepoints specified in the schedule of activities, and as observed or reported spontaneously by study participants.

Medical occurrences that begin after signing of informed consent and before administration of study treatment will be recorded as an AE on the appropriate CRF.

All SAEs will be recorded and reported to the sponsor or designee within 24 hours of learning about the report. All non-serious AEs related to the devices used in the study, as well as Device Complaints, will be reported to the sponsor within 7 working days. The investigator will submit any updates on these events to the sponsor within 24 hours of it being available.

Investigators are not obligated to actively seek AE or SAE in former study participants. However, if the investigator learns of any SAE, including a death, at any time after a participant has completed the final visit of the study, and he/she considers the event to be reasonably related to the study treatment or study participation, the investigator must promptly report the event to the sponsor.

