### *Anticipated Device Effects*

These are known effects of the CoolSculpting Procedure, previously recorded in prior studies as transient and/or temporary effects related to the cold application and/or vacuum pressure inherent in the treatment. Anticipated effects of the device which will not be considered adverse events include:

- inflammation of the subcutaneous fat layer, which is a desired effect of the procedure;
- sensations of coldness, stinging, burning, pinching, or pressure associated with placement of the applicator and the initiation of the cold treatment;
- known skin effects (e.g., blanching; erythema, bruising, purpura, petechiae, swelling, discomfort, tenderness, or soreness at the treatment site, all mild to moderate in nature) which are temporary effects that resolve spontaneously shortly after the procedure;
- localized sensory changes (e.g., numbness, tingling) at the treatment area resolving within 12 weeks of the procedure.

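### Sections 2.9.1, 2.11.1 and 2.18 conflict on a subject who becomes pregnant; if exit is applied at Visit 2 or 3, scheduled safety observation stops 5–7 weeks after her latest CoolMini cycle (minor)

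*Combined protocol and SAP*

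**What the plan says.** Three places deal with the same event.

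- Section 2.9.1 (Screening Visit), on a subject who becomes pregnant during the study: "she will not be treated subsequently with the study device or drug and she will be required to have follow-up photographs and ultrasounds". It gives no date for the imaging and does not mention adverse event (AE) queries or examinations.
- Section 2.11.1 (Treatment Visit 1), step 2, repeats the urine test and excludes a subject with a positive result. Section 2.11.2 has the second CoolSculpting treatment follow the steps of section 2.11.1, and Table 2 schedules a pregnancy test at Visits 2, 3 and 4 as well.
- Section 2.18 (Pregnancy) has the investigator inform her physician and "exit the participant from the study". It gives no timing. The pregnancy itself is still followed: "Details of all pregnancies in female participants will be collected after the start of study treatment through the duration of the pregnancy".

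Other relevant text:

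- Section 2.15.2 defines the As-Treated population as "all treated subjects regardless of whether they become pregnant" and says the Safety population should be identical to it.
- Section 2.18 (Time Period and Frequency) states: "Investigators are not obligated to actively seek AE or SAE in former study participants".
- Section 2.9.1 treats weight change, another reason for leaving the efficacy analysis, differently: "Subjects who do not maintain their weight within 5% will continue in the study, however their data will be excluded from Efficacy analyses".

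**The concern.** A site that exits a subject on the day of a positive test cannot then obtain the imaging that section 2.9.1 requires. A site that images her later has not exited her at that point. With up to three sites, the same event could be handled in different ways.

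What is at stake is safety information. Exit ends the scheduled AE queries and the treatment-site, oral cavity and nerve function examinations. Two device effects in section 6.2 appear, or can be classified, only late. Section 6.2 excludes from AEs "localized sensory changes (e.g., numbness, tingling) at the treatment area resolving within 12 weeks of the procedure"; numbness or tingling becomes an adverse effect only if it lasts beyond 12 weeks. Paradoxical hyperplasia is listed as developing 2–5 months after treatment. A subject who leaves before those times stays in the denominator of the primary safety endpoint without having been observed for either effect. Section 2.13.1 frames that endpoint at the final follow-up visit, which she may never have.

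**Working it through.** The plan gives no figure to reproduce here. The check compares visit windows with the protocol's own clinical thresholds.

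**Inputs from the documents**
- Visit 2 is 6 weeks ± 7 days after CoolMini cycle 1, and Visit 3 is 6 weeks ± 7 days after cycle 2 (sections 2.11.2, 2.11.3).
- Visit 4 is 4–7 weeks after Visit 3 (section 2.11.4).
- Final follow-up is "12 ± 3 weeks post final tx" (Table 2), that is, 9–15 weeks.
- Prolonged sensory alteration means more than 12 weeks; paradoxical hyperplasia means 2–5 months (section 6.2).
- One month is taken as 365.25/12/7 = 4.35 weeks, so 2–5 months is 8.7–21.7 weeks.

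**Time since the latest cycle if exit is applied at the test**
- Visit 2 or 3: 6 − 1 = 5 to 6 + 1 = 7 weeks.
- Shortfall to the sensory threshold: 12 − 7 = 5 to 12 − 5 = 7 weeks.
- Shortfall to the start of the hyperplasia window: 8.7 − 7 = 1.7 to 8.7 − 5 = 3.7 weeks. If a month is taken as 4 weeks, this is 8 − 7 = 1 to 8 − 5 = 3 weeks.

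**Where the timing argument does not apply**
- At Visit 3, cycle 1 is already 5 + 5 = 10 to 7 + 7 = 14 weeks old.
- At Visit 4, cycle 2 is 5 + 4 = 9 to 7 + 7 = 14 weeks old.
- Prolonged erythema (over 2 weeks) and prolonged bruising or swelling (over 1 month, 4.35 weeks) can already be classified by weeks 5–7.

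**How often it could arise.** The documents give neither the number of women of childbearing potential nor a pregnancy rate. Assume 5–15 such women and 2–5% per year on contraception. Then P(at least one pregnancy) = 1 − (1 − rate)^(n × weeks/52). To nominal Visit 3 (week 12):
- n = 5, 2%: 1 − 0.98^(5 × 12/52) = 2.3%.
- n = 15, 5%: 1 − 0.95^(15 × 12/52) = 16.3%.

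A lost event also needs a late effect in that subject, at a rate the documents do not give. With an illustrative 1–5%, the product runs from 0.023 × 0.01 = 0.02% to 0.163 × 0.05 = 0.8%, before allowing for self-report. One missed event would be 1/20 = 5 percentage points in a tabulated incidence at full enrollment.

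**After the fix.** Observation would run to 9–15 weeks after her last cycle instead of 5–7. That passes the start of the hyperplasia window (8.7 weeks). It passes the sensory threshold only if the visit falls after week 12. It does not reach 21.7 weeks.

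**The case against.** The strongest reply is that the rules can be read in sequence: stop treatment, complete the imaging, then exit. Section 2.18 gives no exit date, so this reading satisfies both it and section 2.9.1. Sections 2.15.3.2 and 2.15.3.3 lean the same way. They limit efficacy to subjects followed to the final visit who did not become pregnant, a condition that would be largely redundant if every pregnant subject had already left. Table 2 also helps: the only ultrasound visits after baseline are Visit 3 and the final follow-up, and both carry the AE, treatment-site, oral cavity and nerve checks. This stands as a plausible reading. But the text never states the sequence, and section 2.11.1 step 2, as applied at Visit 2, points the other way. A reader might infer that the plan definitely ends observation at 5–7 weeks. The documents do not support that; it follows only if exit or exclusion is applied at detection.

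The second reply is that much cover survives exit. Known AEs that are serious, related or medically significant are followed (section 2.18). Related serious events learned of later must be reported, the pregnancy is followed to its end, and subjects are encouraged to call the site (sections 2.11.1, 2.11.3). Sensory change needing medical intervention is an adverse effect at any duration (section 6.2). All of this stands, and it limits the gap to non-serious late effects that she does not report.

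Third, a reader might infer that she should be questioned through 5 months. The plan does not secure that for others: a three-treatment subject has her final visit 5 + 9 = 14 to 7 + 15 = 22 weeks after cycle 2, mostly short of 21.7 weeks. Incomplete cover of the hyperplasia window is a general feature of the design, so this is not a defect specific to pregnancy.

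**Conclusion.** The wording conflict is real and spans three sections. If exit or exclusion is applied when pregnancy is detected at Visit 2 or 3, scheduled safety observation stops 5–7 weeks after the latest CoolMini cycle. That is before prolonged sensory change can be classified and before paradoxical hyperplasia is expected, while she remains in the Safety population.

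Severity is minor; correcting it is a cheap improvement. The situation is rare (about 2–16% for any pregnancy by nominal Visit 3, under the stated assumptions), and a lost event is much rarer. This is a feasibility study of up to 20 subjects whose safety endpoint is tabulated. A reader might infer that the efficacy results are affected, but sections 2.15.3.2 and 2.15.3.3 leave pregnant subjects out of efficacy whether or not they stay. Nor do the documents support a claim of material bias in the safety results: they give no late-effect rate, and the cover described above remains.

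**What to change.** 1. In section 2.18 (Pregnancy), replace the exit instruction with three points. Study treatment is discontinued. The participant stays in the study for the scheduled safety assessments (AE query; treatment-site, oral cavity and nerve function examinations) and the section 2.9.1 imaging through the final follow-up, 12 ± 3 weeks after her last treatment and preferably after week 12. The pregnancy is followed to outcome.
2. In section 2.9.1, add the same safety assessments and the same visit to the pregnancy paragraph.
3. In section 2.11.1 step 2, state that exclusion for a positive test applies only before the first treatment, and that a later positive test stops further treatment only. Without this edit, Visit 2 would still carry an exclusion instruction.

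The cost is three wording edits. When pregnancy is found at Visit 2 or 3, the 2-week check after the last treatment is already due, so the one scheduled visit kept is the final follow-up, under 1 hour in Table 2. Sample size, analysis populations and efficacy analysis do not change. A question about late submental enlargement through 5 months could be added to the pregnancy contacts, but it is optional. Removing the imaging requirement and defining an exit visit would also end the conflict if section 2.11.1 were aligned, but would leave the late-effect gap.
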